Neurologic events	See "ischemic stroke," "Overt CNS Injury," "Covert CNS Injury," "Neurological dysfunction without CNS injury," "CNS infarction," and "CNS hemorrhage"
NYHA (New York	Classified as(37):
Heart Association) functional capacity	Class I. Patients with cardiac disease but without resulting limitation of physical activity. Ordinary physical activity does not cause undue fatigue, palpitation, dyspnea, or anginal pain.
capacity	Class II. Patients with cardiac disease resulting in slight limitation of physical activity. They are comfortable at rest. Ordinary physical activity results in fatigue, palpitation, dyspnea, or anginal pain.
	Class III. Patients with cardiac disease resulting in marked limitation of physical activity. They are comfortable at rest. Less than ordinary activity causes fatigue, palpitation, dyspnea, or anginal pain.
	Class IV. Patients with cardiac disease resulting in inability to carry on any physical activity without discomfort. Symptoms of heart failure or the anginal syndrome may be present even at rest. If any physical activity is undertaken, discomfort is increased.
OAC	Oral Anticoagulant (Coumadin or DOAC)
Overt CNS injury	Acutely symptomatic brain or spinal cord injury (NeuroARC Type 1) (29), including:
	Type 1.a Ischemic stroke
	Sudden onset of neurological signs or symptoms fitting a focal or multifocal vascular territory within the brain, spinal cord, or retina, that:

- 3) Persist for ≥24 h or until death, with pathology or neuroimaging evidence that demonstrates either:
 - a) CNS infarction in the corresponding vascular territory (with or without hemorrhage); *or*
 - Absence of other apparent causes (including hemorrhage), even if no evidence of acute ischemia in the corresponding vascular territory is detected

Or

4) Symptoms lasting <24 h, with pathology or neuroimaging confirmation of CNS infarction in the corresponding vascular territory. *Note:* When CNS infarction location does not match the transient symptoms, the event would be classified as covert CNS infarction (Type 2a) and a TIA (Type 3a), but not as an ischemic stroke.

Signs and symptoms consistent with stroke typically include an acute onset of 1 of the following: focal weakness and/or numbness; impaired language production or comprehension; homonymous hemianopia or quadrantanopsia; diplopia; altitudinal monocular blindness; hemispatial neglect; dysarthria; vertigo; or ataxia.

Subtype 1.a.H Ischemic stroke with hemorrhagic conversion

Ischemic stroke includes hemorrhagic conversions. These should be sub classified as Class A or B when ischemic stroke is the primary mechanism and pathology, or neuroimaging confirms a hemorrhagic conversion.

Class A (Petechial hemorrhage): Petechial or confluent petechiae within the infarction or its margins, but without a space-occupying effect

Class B (Confluent hemorrhage): Confluent hemorrhage or hematoma originating from within the infarcted area with spaceoccupying effect

Type 1.b Symptomatic intracerebral hemorrhage

Rapidly developing neurological signs or symptoms (focal or global) caused by an intraparenchymal, intraventricular, spinal cord, or retinal collection of blood, not caused by trauma

Type 1.c Symptomatic subarachnoid hemorrhage

Rapidly developing neurological signs or symptoms (focal or global) and/or headache caused by bleeding into the subarachnoid space, not caused by trauma

Type 1.d Stroke, not otherwise specified

An episode of acute focal neurological signs or symptoms and/or headache presumed to be caused by CNS ischemia or CNS

	hemorrhage, persisting ≥24 h or until death, but without sufficient evidence to be classified as either (i.e., no neuroimaging performed)
	Type 1.e Symptomatic hypoxic-ischemic injury
	Nonfocal (global) neurological signs or symptoms due to diffuse brain, spinal cord, or retinal cell death (confirmed by pathology or neuroimaging) in a nonvascular distribution, attributable to hypotension and/or hypoxia
Pericardial effusion	Pericardial effusion will be classified for severity and time of occurrence according to the following definitions (38):
	Clinically non-relevant:
	Requiring no intervention
	Treated pharmacologically
	Clinically relevant (sub-classified as with or without cardiac tamponade):
	Treated with therapeutic pericardiocentesis
	Treated with surgical intervention
	Requiring blood transfusion
	Resulting in shock and/or death
	Time of occurrence:
	Intraprocedural: during the index procedure
	Acute: <48 hours after the index procedure
	 Late: ≥48 hours after the index procedure
	 Very Late: ≥45 days after the index procedure
	Pericardial Effusion Grading
	Small <10mm
	Moderate 10-20mm
	• Large > 20mm
	Pericardial effusion deemed as small does not meet adverse event reporting criteria.
Patent Foramen Ovale	Patent foramen ovale [PFO] is a remnant of normal fetal anatomy which persists into adulthood and is defined as a communication between the left and right atria at the level of the fossa obalis. PFOs that do not warrant closure do not meet adverse event reporting criteria.
Procedure success	Defined as Technical Success without in-hospital major procedure-related complications (excluding minor device

	embolization) evaluated at hospitalization or at 7 days whichever is first.
Screen failure	Any subject that has signed informed consent but at any point during the process does not fulfill all eligibility criteria will be considered a Screen Failure.
Serious Adverse Device Effect (SADE)	A serious adverse device effect is an adverse device effect that has resulted in any of the consequences characteristic of a serious adverse event.
Serious Adverse Event (SAE)	A serious adverse event is an adverse event that: 1. Led to a death 2. Led to a serious deterioration in the health of the subject that: a. Resulted in a life-threatening illness or injury b. Resulted in a permanent impairment of a body structure or a body function c. Required in-patient hospitalization or prolongation of existing hospitalization d. Resulted in medical or surgical intervention to prevent life-threatening illness or injury or permanent impairment to body structure or a body function 3. Led to fetal distress, fetal death or a congenital abnormality or birth defect.
Systemic Embolism	Acute vascular insufficiency or occlusion of the extremities or any non-CNS organ associated with clinical, imaging, surgical/autopsy evidence of arterial occlusion in the absence of other likely mechanism (e.g., trauma, atherosclerosis, or instrumentation). When there is presence of prior peripheral artery disease, angiographic or surgical or autopsy evidence is required to show abrupt arterial occlusion.(38)
Technical Success	Defined as device success, complete closure or peri-device residual leak ≤5 mm in width on TEE, as evaluated by independent imaging core lab without device-related complications [evaluated post-procedure].
Transient ischemic attack (TIA)	NeuroARC defined (29) as transient focal neurological signs or symptoms (lasting <24 h) presumed to be due to focal brain, spinal cord, or retinal ischemia, but without evidence of acute infarction by neuroimaging or pathology (or in the absence of imaging).

Unanticipated An unanticipated adverse device effect is any serious adverse Adverse Device effect on the health or safety or any life-threatening problem or death caused by, or associated with, a device, if that effect, Effect (UADE) problem, or death was not previously identified in nature, severity or degree of incidence in the investigational plan or application (including a supplementary plan or application), or any other unanticipated serious problem associated with a device that relates to the rights, safety or welfare of subjects. NOTE: An anticipated serious adverse device effect (ASADE) is a serious adverse device effect which by its nature, incidence, severity, or outcome has been identified in the investigational plan or application (including a supplementary plan or application). Use Error Act or omission of an act that results in a different medical device response than intended by the manufacturer or expected by the user. NOTE 1: Use error includes slips, lapses and mistakes. NOTE 2: An unexpected physiological response of the patient does not itself constitute a use error. Vascular Based upon VARC-3(33) definitions, classified as major or minor complications and sub-classified as access site-related or non-access site-related **Major Vascular Complications** Includes One of the Following: Aortic dissection or aortic rupture Vascular (arterial or venous) injury (perforation, rupture, dissection, stenosis, ischemia, arterial or venous thrombosis including pulmonary embolism, arteriovenous fistula, pseudoaneurysm, hematoma, retroperitoneal hematoma, infection) or compartment syndrome resulting in death, VARC type ≥2 bleeding, limb or visceral ischemia, or irreversible neurologic impairment Distal embolization (non-cerebral) from a vascular source resulting in death, amputation, limb or visceral ischemia, or irreversible end-organ damage Unplanned endovascular or surgical intervention resulting in death, VARC type ≥2 bleeding, limb or visceral ischemia, or irreversible neurologic impairment Closure device failure resulting in death, VARC type ≥2 bleeding, limb or visceral ischemia, or irreversible neurologic impairment **Minor Vascular Complications** Includes One of the Following:

	 Vascular (arterial or venous) injury (perforation, rupture, dissection, stenosis, ischemia, arterial or venous thrombosis including pulmonary embolism, arteriovenous fistula, pseudoaneurysm, hematoma, retroperitoneal hematoma, infection) not resulting in death, VARC type ≥2 bleeding, limb or visceral ischemia, or irreversible neurologic impairment Distal embolization treated with embolectomy and/or thrombectomy, not resulting in death, amputation, limb or visceral ischemia, or irreversible end-organ damage Any unplanned endovascular or surgical intervention, ultra-sound guided compression, or thrombin injection, not resulting in death, VARC type ≥2 bleeding, limb or visceral ischemia, or irreversible neurologic impairment Closure device failure‡ not resulting in death, VARC type ≥2 bleeding, limb or visceral ischemia, or irreversible neurologic impairment
Vitamin K Inhibitor	Coumadin/warfarin

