6.3 Conformal Prague Study

The Prague Feasibility Study was designed to evaluate the safety and performance of the CLAAS System. The study was performed at a single center in Prague, Czech Republic (Homolka Hospital). Subjects were treated using a conscious sedation protocol which featured Intracardiac Echo (ICE) guided transseptal puncture and device deployment with TEE confirmation prior to final release. Subjects were followed through hospital discharge and through serial follow-up assessments post index procedure at discharge, 7 days, 45 days including TEE imaging, 6 months, and 12 months including TEE imaging. The primary safety endpoint of the study is freedom from major adverse events while the primary performance endpoint is LAA closure success. A total of 15 subjects were recruited from October 2019 through January 2020, when the study was paused due to the COVID-19 Pandemic. Results of these initial 15 subjects were summarized by Turagam et al. (27)

A total of 15 subjects (age 71.3±10.8 years, 33% men, CHA2DS2-VASc of 4.1 ±1.7, HAS-BLED 3.4 ±1.4) underwent LAAC, 100% successfully. There were no procedure/device-related complications requiring intervention. Asymptomatic pericardial effusion occurred in 2 subjects. The 45-day, 6-month, and 12-month follow-up imaging in 11, 9, and 13 subjects, respectively, revealed adequate LAA seal (leak <5 mm) in all subjects; device-related thrombus was detected in 1 subject at 6 months. Over 1-year follow-up, there were no ischemic strokes and 1 minor bleed. Non procedure-/device-related death occurred in 2 subjects.

Following removal of COVID-19 restrictions, an additional 4 subjects were treated. Preliminary results indicate successful closure without procedural complications in all subjects. Additional details on this study will be available in the study Investigator Brochure.

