8.5.1 Primary Safety Endpoint

A composite of:

- Major Procedure-Related Complications including (identified within 12 months of procedure and adjudicated as procedure related):
 - a. cardiac perforation
 - b. pericardial effusion requiring drainage
 - c. ischemic stroke
 - d. device embolization
 - e. major vascular complications
- Major bleeding through 12 months post procedure or
- All-cause death 12 months post procedure

All definitions are provided for all components in Appendix A. All events will be adjudicated by the independent Clinical Events Committee (CEC).

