12.1 Reportable Events by Investigational Sites

Investigators are responsible for reporting and assessing the following events:

- All serious adverse events
- All device and procedure-related adverse events
- UADE (Unanticipated Adverse Device Effects)/ USADE (Unanticipated Serious Adverse Device Effects)
- Pre-procedure events (e.g., events related to pre-procedure medication changes)
- All adverse events of special interest. The following events, regardless of seriousness or relatedness will be collected:

- Bleeding events
- Embolic events (e.g., stroke, TIA, systemic embolism)
- Neurologic events
- Device embolizations
- Device Related Thrombus
- Myocardial Infarction
- o Pericardial Effusion
- Vascular Complication

The following clinical events will not be considered reportable adverse events, unless the investigator considers the event to be related to the investigational device or procedure, or an AE of special interest:

- Pre-existing medical conditions or a repeat of symptoms are not required to be reported as adverse events *unless* there is a worsening in severity or frequency during a study.
- Planned procedures (scheduled prior to the index procedure) that occur after the index procedure are not considered reportable AEs. Complications from such procedures, however, must be reported.
- Abnormal non-cardiac laboratory findings are not considered a reportable AE unless:
 - The investigator determined that the finding is clinically significant, OR
 - The abnormal laboratory finding required intervention, OR
 - The abnormal laboratory finding required termination of the subject's participation in the study.

Investigators shall report relevant adverse events as follows:

- All sections of the Adverse Event CRF shall be completed for each applicable AE
- Each unique event/diagnosis must be documented separately
- Assess the relationship of the event to the investigational device and procedure
- The AE Term should be reported as a medical diagnosis if available, rather than clinical symptoms
- Death events should not be recorded as an adverse event, but as an outcome to a single serious adverse event
- The AE CRF must be reviewed and signed by the investigator
- If an AE is deemed not to be related to the device, procedure implant or medications and is not cardiovascular or neurological in nature AND; does not meet serious adverse criteria it does not need to be reported.

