13.2 Clinical Events Committee (CEC)

An independent Clinical Events Committee (CEC) will adjudicate all site-reported potential endpoint events and any other events the Sponsor deems necessary, in an ongoing fashion during the trial. Relationship of these events to the assigned device and/or procedure will also be adjudicated, and sub-classified as implant-related, delivery system-related or study medication related (anti-coagulation or antithrombotic) or related to a comorbid condition. The committee will include at least three voting members consisting of qualified physicians (cardiologists, interventional cardiologists, electrophysiologists and/or neurologist) experienced in clinical trials who are otherwise independent of the Sponsor and the conduct of the study. Members will also

be selected with consideration of their experience in the conduct of clinical trials and prior participation on a Clinical Events Committee.

Members will not have scientific, financial, or other conflicts of interest related to Conformal Medical, Inc. or the Investigator(s). The CEC will operate and conduct all meetings and event reviews independent of the Sponsor unless specific expert knowledge regarding the characteristics or function of the study device is requested by the CEC from the Sponsor.

The adjudication process, event definitions and required source document materials for each type of event will be pre-specified prior to the onset of the trial. The CEC members will review data collected from all relevant medical records, as well as all imaging study reports associated with an event to perform adjudication. All adjudication decisions will be made by the CEC in an independent and blinded fashion (to the extent possible) based upon review of all available medical evidence. Treatment assignment to investigational device/control device will be deidentified in any source documentation reviewed by the CEC to maintain blinding and reduce any potential bias.

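### Appendix A exempts small (<10 mm) pericardial effusions from adverse event reporting, while Section 12.1 collects pericardial effusions of any size

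*Protocol*

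**What the plan says.** Three parts of the protocol bear on which effusions are reported.

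- **Appendix A, pericardial effusion entry.** Effusions are classified by clinical relevance and also graded by size: small under 10 mm, moderate 10-20 mm, large above 20 mm. The entry closes with: "Pericardial effusion deemed as small does not meet adverse event reporting criteria". In the relevance classification, an effusion "Treated with therapeutic pericardiocentesis", treated surgically, requiring transfusion, or leading to shock or death is clinically relevant, with or without tamponade. That class has no size limit.
- **Section 12.1.** For events of special interest: "The following events, regardless of seriousness or relatedness will be collected". The list that follows includes "Pericardial Effusion" with no size qualifier.
- **Section 8.5.1.** One component of the primary safety composite is "pericardial effusion requiring drainage", if adjudicated as procedure related. It carries no size limit, and the section sends the reader to Appendix A for component definitions.

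Under Section 13.2 the Clinical Events Committee (CEC) "will adjudicate all site-reported potential endpoint events", together with any others the sponsor considers necessary.

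**The concern.** Sections 12.1 and Appendix A give opposite answers for the same finding, and no sentence says which prevails. Sites will meet the question routinely. Section 9.7 requires a pre-discharge transthoracic echocardiogram specifically to look for effusion, and imaging is repeated at 45 days and 12 months. Small effusions are a realistic finding with this device: for the 15 subjects of the feasibility study in Section 6.3 the protocol reports "Asymptomatic pericardial effusion occurred in 2 subjects", although it does not give their sizes.

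The adverse event tables in Section 14.6 are built from site-reported events. If some sites follow Section 12.1 and others Appendix A, the effusion counts by arm reflect reporting practice as well as the devices. Section 8.2.2 describes the trial as unblinded, so equal practice in the two arms cannot be taken for granted.

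There is a second, smaller problem. The exemption turns on size alone, so on its wording it reaches a small effusion that was drained, which is a primary safety event.

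**Working it through.** No arithmetic applies. The check is to run three hypothetical effusions through the current text. The sizes are illustrative.

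| Case | Section 12.1, special interest | Appendix A size sentence | Other reporting routes | Primary safety component? |
|---|---|---|---|---|
| A. 6 mm, no treatment, stable | Collected | Exempt | None beyond Section 12.1 itself | No |
| B. 8 mm, drained, no tamponade | Collected | Exempt | Serious adverse event if drainage meets the definition in Section 12.2; perforation or bleeding if those definitions are met | Yes, if procedure related |
| C. 8 mm with haemodynamic instability, drained | Collected | Exempt | Serious adverse event; tamponade is BARC 3b, and Appendix A asks for all bleeding events to be reported | Yes, if procedure related |

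**Case A** is a plain contradiction. Section 12.1 has its own list of findings that need not be reported. Small effusions are not on it, and that list gives way when an event is of special interest. Nothing there imports the Appendix A exemption. A site following Section 12.1 reports the effusion; a site following Appendix A has no duty to.

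**Case B** shows the clash with the endpoint. The Appendix A entry itself makes a drained effusion clinically relevant at any size, and its last sentence then ignores that class. The separate routes will usually bring the event in, but each depends on its own definition being met.

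**Case C** is well covered. Appendix A defines tamponade by haemodynamic instability, not by millimetres, so the bleeding and serious-event routes apply whatever the size.

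A neighbouring entry shows the kind of qualifier that is absent. The patent foramen ovale exemption in Appendix A is limited to those that do not need closure. The effusion exemption has no comparable limit, which suggests a drafting omission.

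**The case against.** The strongest reply is that the primary endpoint is protected by other rules. Section 12.1 requires all serious and all device- or procedure-related adverse events, and asks for each diagnosis to be documented separately. Exempting the term small effusion therefore does not exempt a tamponade, a bleed or a perforation. Procedural and follow-up echocardiograms go to an independent core laboratory (Section 13.4), the sponsor can refer further events to the CEC (Section 13.2), and study endpoints are fully source-verified (Section 16.1). This largely stands: few drained or tamponading effusions are likely to be lost. It does not remove the conflict, because these routes also disagree with an unqualified exemption. It also does nothing for the untreated small effusion.

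A second reply is that 10 mm is the protocol's working threshold. It appears in the echocardiographic exclusion criteria, in the triggers for further echocardiography, and in Sections 9.9 and 9.11, where a non-trivial effusion is one above 10 mm. Appendix A may therefore be meant to narrow the special-interest term. That is plausible for untreated effusions, but no text says so, and it would still leave the drained small effusion unexplained.

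A reader might also infer more than the text supports:

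- **That reporting a small effusion is forbidden.** Appendix A only removes the duty to report.
- **That the site decides what is small.** The entry does not say who grades.
- **That a drained, tamponading effusion counts as two primary events.** It meets the composite by more than one route, but a subject counts once.
- **That the effect can be sized from the feasibility data.** The 2 of 15 in Section 6.3 are asymptomatic effusions; the 1 of 42 in Section 6.4 is an effusion requiring treatment in a different study. Neither comes with a size, so the comparison says nothing about a 10 mm rule.

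**Conclusion.** The contradiction is in the current text and should be corrected. Its main consequence is for the site-reported effusion rates by arm, which are not well defined while two reporting rules coexist. Uniform under-reporting would shrink any true absolute difference between arms; differential under-reporting would bias it. The documents do not show that reporting would differ by arm, only that nothing in the two rules prevents it.

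The consequence for the primary safety endpoint is limited. A reader might infer that the non-inferiority test against the 5.8% margin is materially at risk. The documents do not support that: serious-event, bleeding and perforation reporting overlap with the exempted cases, and the protocol gives no rate of drained effusions under 10 mm from which an effect could be computed. If true event rates and losses were equal in both arms, the expected difference would not move at all.

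This conclusion rests on reading the Appendix A sentence as written, and on no other passage giving one rule precedence. None does.

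**What to change.** Reconcile Section 12.1 and the Appendix A entry into one reporting rule, stated identically or by cross-reference, that:

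1. says whether untreated, clinically non-relevant effusions under 10 mm are collected as events of special interest; and
2. limits any size exemption to effusions that are clinically non-relevant as the same entry defines it, so that any effusion that is drained, operated on, transfused, associated with tamponade or shock, otherwise serious, or a potential endpoint event is reported and sent to the CEC regardless of size.

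This concerns reporting only and changes nothing in how an effusion is managed. The cost is one sentence in each place and a reminder to sites. Because enrolment began in June 2022, it would be sensible also to check small effusions already seen on protocol imaging against the reconciled rule, so that both arms are counted the same way throughout.
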